4.4.2 Blinding

Investigator blinding will be accomplished by using a Treating Investigator to administer the treatments and a Blinded Evaluator, to whom randomization and treatment are concealed, to conduct the blinded assessments. The Blinded Evaluator is not allowed to discuss treatments with the Treating Investigator or subjects. All study related documents that contain information regarding the treatment of subjects should not be available to the Blinded Evaluator. Safety assessments will be performed by non-blinded personnel as treatment-related AEs are expected to occur during a few days after treatment, thereby revealing which subjects has received the study product.

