4.4.3 Emergency unblinding

Not applicable as the Treating Investigator is unblinded.

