8.1 Assessment of AEs by direct question to subject and evaluation of subject

Safety evaluations for this study include an interview of the subjects at each visit to obtain information about any medical occurrence that meets the definition of an AE. Each subject should be questioned about AEs at each study visit following the screening visit. Information on AEs can also be obtained from signs and symptoms detected during each examination by the Investigator or designee, which should include visual inspection of the treatment area.

AEs must be documented in the source document and eCRF without regard for cause or relation to investigational product. If in the process of the interview, additional information regarding medical history or pre-planned medical or surgical procedures is revealed, it must be documented in the source document(s) and eCRF.

It is the responsibility of the Treating Investigator to determine severity of the AE and relatedness of the event to the study product.

A series of horizontal black bars of varying lengths and positions on a white background, suggesting redacted text. The bars are irregular in length and position, creating a stepped effect across the page. There are small black squares at the far left and right edges of the bars.

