### 2.5.2 Adverse events

AE terms will be coded using MedDRA dictionary. A treatment-emergent AE (TEAE) is defined as an AE with a start date and time on or after the first study product injection. If relationship to treatment is missing, the event will be conservatively summarized as being related to study product. If intensity is missing, a separate category of missing intensity will be included in the summary table, and no imputation of intensity will be performed. Through the data cleaning process, all attempts will be made to avoid missing values for relationship and intensity.

All AEs will be presented in a by-treatment and by-subject listing, detailing the verbatim term given by the investigator, the preferred term (PT), system organ class (SOC), onset date, end date, intensity, outcome, relationship to study product, relationship to study product injection procedure, action taken with study drug, other action taken, affected treatment area, seriousness and criteria for seriousness. Serious AEs will be presented in a separate listing.

Time to onset of an AE will be derived as the start date minus date of most recent treatment. If the start date is missing, it will be assumed that the AE started on the day of most recent treatment.

Duration of an AE will be derived as the stop date minus the start date + 1. If the start date is missing, it will be assumed that the AE started on the day of most recent treatment. Missing stop date will not be imputed and therefore no duration will be calculated in these cases. Instead, the number of AEs that were ongoing at the end of the study will be given.

An overall summary of AEs will be presented by treatment. The summary will include the total number of events, frequency counts and percentages of subjects with:

- Any TEAE

- Any AE related to product and/or injection procedure
- Unrelated TEAEs
- No TEAEs reported

Summaries of related AEs (including the total number of events, frequency counts and percentages of subjects) will be displayed by treatment and treatment occasion according to the following:

- All AEs by SOC and PT in descending order of frequency (the combined frequency of both treatments)
- All AEs by SOC, PT, and maximum intensity (mild, moderate, or severe)
- All AEs by SOC, PT, and action taken (none, medical treatment, non-pharmacological treatment, subject withdrawn)

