For related AEs, the number of days to onset and duration of event will be summarized by SOC and PT, using mean, SD, minimum, maximum, and median statistics.

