#### 2.5.5 Exploratory safety endpoints

- Related AEs by SOC, PT and maximum intensity will be separately summarized for the following subgroups:
  - Study site
  - Injection volume
  - Fitzpatrick skin types (I-III, IV and V-VI)
- [REDACTED].

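### As most naturally read, SAP 2.5.2 tabulates adverse events by SOC and PT only when they count as related, so no visible table shows all-cause TEAEs by term and arm.

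*SAP*

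**What the plan says.** The lead-in to the term-level tables in SAP 2.5.2 reads "Summaries of related AEs (including the total number of events, frequency counts and percentages of subjects) will be displayed by treatment and treatment occasion". Three bullets follow: frequency by SOC and PT, the same by maximum intensity, and the same by action taken. The first begins "All AEs by SOC and PT in descending order of frequency", and the other two also refer to all AEs. The lead-in and the bullets therefore name different populations.

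The neighbouring outputs are limited explicitly. The onset and duration summaries in SAP 2.5.2 open with "For related AEs, the number of days to onset and duration of event will be summarized by SOC and PT". The subgroup tables in SAP 2.5.5 are described as "Related AEs by SOC, PT and maximum intensity will be separately summarized for the following subgroups".

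On who decides relatedness, Protocol 8.1 states: "It is the responsibility of the Treating Investigator to determine severity of the AE and relatedness of the event to the study product". Protocol 4.4.3 dismisses emergency unblinding with "Not applicable as the Treating Investigator is unblinded", and Protocol 4.4.2 adds "Safety assessments will be performed by non-blinded personnel". SAP 1.5 has the Sponsor assess causality as well and resolves any disagreement as related. SAP 2.5.2 counts a missing relationship as related.

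The safety objective in Protocol 3.1.3 and SAP 1.2.3 is to evaluate all AEs at all visits, with no restriction by cause. The exploratory objective in SAP 1.2.4, on consistency of AE data across subgroups, has no such restriction either.

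**The concern.** Randomisation protects the comparison of all-cause event rates between arms. It does not protect a comparison restricted after randomisation by a judgement that can depend on knowing the product. The trial sets an investigational filler against a comparator filler, and the person making the site-level causality call knows which was injected. If attribution differs by arm, a related-only table can show a difference where none exists or shrink one that does. An imbalance in a specific term that was mostly called unrelated would not be seen by term in any visible table.

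The AE outputs are descriptive, and no test on AEs is visible. What is at stake is how far a side-by-side reading of the safety tables can be trusted, in a study meant to support a marketing application. The primary efficacy analysis is not affected.

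**Working it through.** The plan gives no figure on this point to reproduce. The check has three steps: which events each output covers, what removes an event from the tables, and how much that could matter.

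**1. Coverage of each visible AE output**

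| Output | Events covered | Broken down by term? |
|---|---|---|
| Overall summary by arm (SAP 2.5.2) | Any TEAE, related AEs, unrelated TEAEs, no TEAE | No |
| Frequency, maximum-intensity and action-taken tables (SAP 2.5.2) | Lead-in: related; bullets: all | Yes |
| Onset and duration (SAP 2.5.2) | Related | Yes |
| Subgroup tables (SAP 2.5.5) | Related | Yes |
| AE listing and separate SAE listing (SAP 2.5.2) | All AEs; serious AEs | Listed, not tabulated |
| Diary symptoms (SAP 2.5.3, Protocol 10.5) | Pre-defined symptoms, no causality filter visible | By symptom |

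The bullets specify how the summaries named in the lead-in are laid out, so the natural meaning of their wording is all *related* AEs. The onset, duration and subgroup outputs point the same way. On that reading no row gives all-cause TEAEs by SOC/PT and arm. If all AEs were intended, the lead-in is wrong. Either way the text needs correcting.

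**2. What removes an event**

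Under SAP 1.5 and 2.5.2, an event counts as related if the investigator says yes for the product or the injection procedure, or if the Sponsor's assessment is related, or if the relationship is missing. It leaves the term-level tables only when investigator and Sponsor both call it unrelated.

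**3. Illustration (every rate is assumed; none comes from the documents)**

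Let p be the true incidence of a term, the same in both arms. Let q be the share of cases the investigator calls related, and s the share of the remainder that the Sponsor makes related, also the same in both arms. Then

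tabulated rate = p × [1 − (1 − q)(1 − s)].

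With p = 0.10, q = 0.80 for Kysse and q = 0.50 for control:

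| s | Kysse | Control | Ratio |
|---|---|---|---|
| 0 | 0.10 × [1 − 0.20 × 1] = 0.080 | 0.10 × [1 − 0.50 × 1] = 0.050 | 1.6 |
| 0.5 | 0.10 × [1 − 0.20 × 0.5] = 0.090 | 0.10 × [1 − 0.50 × 0.5] = 0.075 | 1.2 |
| 1 | 0.10 × [1 − 0.20 × 0] = 0.100 | 0.10 × [1 − 0.50 × 0] = 0.100 | 1.0 |

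The same formula with other investigator shares gives:

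| q, Kysse vs control | Ratio, s = 0 | Ratio, s = 0.5 |
|---|---|---|
| 0.90 vs 0.90 | 1.00 | 1.00 |
| 0.90 vs 0.70 | 0.090/0.070 = 1.29 | 0.095/0.085 = 1.12 |
| 0.90 vs 0.50 | 0.090/0.050 = 1.80 | 0.095/0.075 = 1.27 |
| 0.50 vs 0.80 | 0.050/0.080 = 0.63 | 0.075/0.090 = 0.83 |

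Because p cancels, the ratio does not depend on how common the term is. An all-TEAE table would show 10% vs 10% in every row.

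**The case against.** The strongest reply is that the plan's causality rule is deliberately inclusive. A reader might infer that the unblinded investigator alone decides what enters the tables. SAP 1.5 does not support that: the Sponsor can add an event that the investigator called unrelated and cannot remove one that the investigator called related. This stands, and it is why the illustration runs down to a ratio of 1.0. It does not close the gap, because events that both call unrelated still drop out, and the visible text does not say whether the Sponsor's assessor is blinded. That assessor can be assumed neither blinded nor unblinded.

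A reader might also infer that unrelated events are hidden. They are not. The overall summary counts unrelated TEAEs by arm, and the listing shows every AE with its term, intensity and relationship. Only a term-level table is missing.

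Third, the local reactions most expected of a filler are tabulated by symptom from the subject diary with no visible causality filter. That is a real safeguard, but it covers only pre-defined symptoms in about the first month after treatment (4 weeks in the objectives, 30 days in Protocol 8.7.3 and 10.5). Other AEs over the 48-week follow-up are outside it.

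Finally, parts of Protocol 10.5 and SAP 2.5.4 are redacted and the endpoint list in SAP 1.6 is not visible, so an all-cause table specified there cannot be excluded. SAP 2.5.2, the dedicated AE section, shows no redaction.

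**Conclusion.** The point holds as a reporting gap with a wording conflict. As most naturally read, the SAP gives no visible SOC/PT table of all-cause TEAEs by arm, which falls short of its own objective to evaluate all AEs. The term-level tables that it does give rest on a causality filter that partly depends on unblinded judgement.

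The size cannot be read from the documents. Under the assumed 80% vs 50% attribution, the spurious ratio runs from 1.6 with no Sponsor reclassification, through 1.2 at half, to none if the Sponsor reclassifies everything. It disappears equally if investigators attribute alike in both arms. These figures show what the filter could do. They are not evidence that attribution will differ, and the documents do not support a claim that the safety results will be biased or in which direction.

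The conclusion rests on reading the bullets as governed by their lead-in, and on no all-cause table standing in redacted text. The correction is worth making because it is cheap. It bears on the safety display only.

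**What to change.** Change the lead-in in SAP 2.5.2 to *Summaries of all TEAEs, and separately of related AEs*, and make the bullets agree with it. Produce the SOC/PT table and the SOC/PT/maximum-intensity table by arm for both populations, as descriptive displays, with the related-AE tables kept as a subset.

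The cost is SAP wording and two extra tables. Protocol 8.1 already has AEs documented whatever their cause, and SAP 2.5.2 already codes them in MedDRA, so no new data and no change in conduct are needed. If the database is already locked, SAP 2.1 calls for the change to be documented in the clinical study report.

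The change removes the attribution filter only. Safety assessments are still made by non-blinded personnel and the Treating Investigator still grades severity, so unblinded ascertainment and intensity grading would remain in the new tables.

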4.1 General outline

This is a randomized, controlled, evaluator-blinded, multi-center study to evaluate the effectiveness and safety of *Restylane® Kysse* for lip augmentation and correction of perioral rhytids. Approximately 280 subjects will be randomized in a 2:1 ratio of treatment to control and treated. Approximately 187 subjects will be treated with *Restylane® Kysse* and 93 subjects will receive the control in the lips and perioral rhytids for 48-weeks. All randomized subjects' lips will have a MLFS score of 1 (Very Thin) or 2 (Thin). The upper lip and lower lip scores do not have to be equal as long as each score is 1 or 2.

At least 42 subjects enrolled and treated will be FST IV through VI. This includes up to 21 subjects with FST V to VI who do not have to meet the inclusion criteria for MLFS.

Investigator blinding will be accomplished by using a Treating Investigator to administer the treatments and a Blinded Evaluator, to whom randomization and treatment are concealed, to conduct the blinded assessments. Safety assessments will be performed by non-blinded personnel.

Eligible subjects randomized to receive treatment will be injected by the Treating Investigator at Day 1. The method of injection is at the discretion of the Treating Investigator and will be recorded. Sufficient amount of product should be injected to achieve optimal correction of the lips, in the opinion of the Treating Investigator and subject. Optimal appearance is defined as at least 1 MLFS step improvement from Baseline and best correction that can be achieved as agreed by the Treating Investigator and the subject. Touch-up treatment may be administered after 4 weeks if deemed necessary to obtain optimal aesthetic result; this decision should be agreed upon by the Treating Investigator and the subject. Touch-up treatment will not be performed if the subject has a disease or condition described in the exclusion criteria, or an ongoing treatment-related AE that in the opinion of the Treating Investigator would be worsened by a touch-up. It is recommended that the dose should not exceed 1.5 mL in each lip (including vermillion, vermillion border and cupid's bow) per treatment session. The study product may also be injected for optimal correction of the upper perioral rhytids, philtral columns, and/or oral commissures. The recommended maximum injected volume per subject and treatment is 6 mL (i.e. 3 mL for lips and 3 mL for perioral area).

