Subjects will have in-clinic follow up visits at 2, 4, 8, 16, 24, 32, 40, and 48 weeks after the last injection. If a touch-up is performed, a second 2-week and 4-week follow-up visits should be scheduled. At the 48-week visit after all study procedures for the visit are completed, subjects can receive an optional additional treatment if optimal aesthetic improvement is not maintained with *Restylane® Kysse*. If re-treatment is performed, a second 2-week and 4-week follow-up visits should be scheduled. In addition to the clinic visits, phone visits will also occur as specified in the study flow chart below.

A Study Flow Chart is provided on the next page.

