8.7.4 Reporting of adverse events

Adverse event reporting on each subject shall start at screening visit after the signature of the ICF. The reporting shall continue during each follow-up visit (including telephone contacts and extra visits between planned visits) until the last scheduled visit in the study.

All AEs, non-serious as well as serious, are to be reported as an AE in the eCRF.

Follow-up information and data missing in the initial SAE reporting shall be gathered as soon as possible and reported immediately but not later than 24 hours of awareness of the new data. Complete and adequate information on each SAE is required. All attempts to obtain this information, including dates for follow-up activities, must be documented by the Investigator or designated study staff.

Supporting documentation to be provided with the SAE report:

- Concomitant medication form
- Concomitant procedure/treatment form
- AE form
- Medical history form
- Any other relevant supporting documentation (e.g. hospital notes, death certificate, autopsy reports etc.)

The SAE form must be signed and dated by the Investigator. If the initial 24-hour SAE report does not contain full information or if it is made without using the SAE form the fully completed and signed SAE form shall be e-mailed to the Sponsor. A copy of the fully completed SAE form shall be kept at the site.

In addition, the Investigator shall report SAEs to the responsible IRB without undue delay, if applicable according to national regulations. The Investigator is responsible for checking what reporting procedures are applicable for his/her IRB regarding SAEs and final report of the outcome of the study and to comply with such reporting procedures during the study period. For non-urgent complementary information not possible to send by e-mail or fax, please use surface mail.

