## 2.5 Safety Analysis

### 2.5.1 Extent of exposure

The number of subjects receiving initial treatment, touch-up treatment, and Week 48 retreatment respectively, will be presented by treatment group and treatment occasion (i.e. initial treatment or retreatment) as well as injection volume and other relevant injection characteristics, such as injection depth, injection method.

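### Related-AE percentages by treatment occasion set about 48 to 52 weeks and up to two injection sessions against one re-treatment session with about 4 weeks of visible follow-up

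*SAP*

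**What the plan says.** SAP 2.5.2 plans three sets of related-AE tables: by SOC and PT, by maximum intensity, and by action taken. It says: "Summaries of related AEs (including the total number of events, frequency counts and percentages of subjects) will be displayed by treatment and treatment occasion". SAP 2.5.1 gives the term two levels: "treatment occasion (i.e. initial treatment or retreatment". That section counts touch-up recipients separately, but touch-up is not a level of occasion. The natural reading is that it belongs to the initial occasion.

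Protocol 4.1 sets the follow-up:

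- Initial treatment: "Subjects will have in-clinic follow up visits at 2, 4, 8, 16, 24, 32, 40, and 48 weeks after the last injection".
- Touch-up: "Touch-up treatment may be administered after 4 weeks if deemed necessary to obtain optimal aesthetic result". The 2- and 4-week visits are then repeated.
- Re-treatment: "At the 48-week visit after all study procedures for the visit are completed, subjects can receive an optional additional treatment". Then: "If re-treatment is performed, a second 2-week and 4-week follow-up visits should be scheduled". The visible text names no later clinic visit.

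Under Protocol 8.7.4, AE reporting runs "until the last scheduled visit in the study".

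On timing, SAP 2.5.2 measures onset from the most recent treatment and adds: "For related AEs, the number of days to onset and duration of event will be summarized by SOC and PT". It does not say whether that summary is split by occasion. SAP 2.1 bases percentages on the number of observations at the time point. The visible SAP has no common post-injection window, no patient-time rate and no caveat for the by-occasion tables. Missing relationship is counted as related.

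**The concern.** A by-occasion layout invites the reader to judge whether repeat injection is as well tolerated as first injection. Two features of the columns push the same way. The initial column has far longer to accumulate events, and it can contain two injection sessions against one. If the true risk per injection were identical, the re-treatment column would be expected to show an equal or lower percentage, never a higher one. Counting events of missing relationship as related adds slightly more to the longer window.

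The effect is strongest in the PT rows for late-onset events. A near-empty re-treatment cell there reflects short observation, but it could be read as reassurance. The report is intended for a marketing application, so these tables may be used to describe repeat-treatment safety.

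**Working it through.** The documents give no AE rate, onset distribution or touch-up share. Only the windows come from the plan. The rates below are assumptions used to show a range.

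**1. Windows (Protocol 4.1).**
- Initial occasion: 48 weeks = 336 days, or 48 + 4 = 52 weeks = 364 days with a touch-up at about week 4.
- Re-treatment: 4 weeks = 28 days.
- Ratios: 48/4 = 12 and 52/4 = 13. Equivalently, 28/336 = 8.3% and 28/364 = 7.7%.
- Clinic visits: 8 (10 with touch-up) against 2.

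**2. Check against the stated duration (Protocol 4.3, approximately 15 months).**
- Longest visible path: 30 days of screening + 4 + 48 + 4 weeks = 60.3 weeks = 13.9 months.
- Taken literally, 15 months is 65.2 weeks. After screening, touch-up and 48 weeks, this leaves 65.2 − 4.3 − 4 − 48 = 8.9, or about 9 weeks, after re-treatment.
- The ratio is then 48/9 = 5.3 to 52/9 = 5.8, so the imbalance remains on that reading.

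**3. Window effect alone.** Assume a true 48-week related-AE risk of 20% and the same risk after re-treatment.
- Constant hazard: 1 − (1 − 0.20)^(4/48) = 1.8% in 4 weeks, or 1 − 0.80^(9/48) = 4.1% in 9 weeks.
- If a share f of affected subjects has onset within 4 weeks, the re-treatment column shows f × 20%:

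| f | Initial | Re-treatment | Gap (points) |
|---|---|---|---|
| 100% | 20% | 20% | 0 |
| 95% | 20% | 19% | 1 |
| 90% | 20% | 18% | 2 |
| 75% | 20% | 15% | 5 |
| constant hazard | 20% | 1.8% | 18.2 |

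**4. A late-onset event type.** Assume a constant 0.5% per 4 weeks. Over 48 weeks this gives 1 − 0.995^12 = 5.8%, against 0.5% in 4 weeks.

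**5. Session effect alone.** Assume all onsets are early, the risk per session is r = 20%, sessions are independent and a share s has a touch-up. The initial occasion shows (1 − s)r + s[1 − (1 − r)²].
- s = 25%: 24%
- s = 50%: 28%
- s = 75%: 32%

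Re-treatment shows 20% in each case. Equal windows alone would therefore not make the columns comparable while touch-up stays in the initial occasion.

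**6. Onset summary.** The clock restarts at each treatment, so an event captured by the visible schedule after re-treatment can show an onset of at most about 28 days. After the last initial or touch-up injection it can show up to about 336 days.

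**The case against.** The strongest reply is that these tables contain related AEs only, and Protocol 4.4.2 anticipates treatment-related events in the first days after injection. If so, four weeks captures nearly all of them and the window effect is close to nil. This stands as a limit on size. It is an expectation given to explain why safety staff are unblinded, not an onset distribution. It does not help with late-onset rows, and it does not touch the session effect.

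Other replies also carry weight:

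- The synopsis asks for related events with onset after participation to be reported if the investigator learns of them. That is passive capture, and the documents do not say whether such events reach the tables.
- The diary runs for about 4 weeks after each treatment, so expected post-treatment events have near-equal windows. They are summarised separately from AEs (SAP 2.5.3).
- No test or formal contrast between occasions is planned, and listings give onset dates. The issue is how a descriptive table will be read.
- The schedule of events and flow chart are not visible, and Protocol 4.1 mentions phone visits. About 4 weeks is the likely follow-up, but it is not certain.

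A reader might infer that re-treatment is bound to look materially safer, or that the plan pools days to onset across occasions. The documents support neither. The size turns on quantities they do not give, and SAP 2.5.2 is silent on pooling.

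**Conclusion.** The by-occasion display compares unequal observation times and unequal numbers of sessions, and nothing visible in SAP 2.5.2 adjusts for either. The direction is fixed: at equal true risk per injection, the comparison can only favour re-treatment. Self-selection of subjects who take the optional re-treatment is a separate matter and could act either way.

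The size is open. Under the assumed 20% risk, the window effect ranges from 0 to about 18 points, and it is 0 to 2 points if at least 90% of affected subjects have early onset. The session effect is 4 to 12 points for touch-up shares of 25% to 75%. For late-onset events, the re-treatment column is nearly uninformative whatever the overall gap.

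This rests on three readings: touch-up belongs to the initial occasion, scheduled follow-up after re-treatment is about 4 weeks, and 48 weeks of follow-up applies to completers. The point concerns descriptive safety tables, not the primary analysis, and is worth making because the remedy is cheap.

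**What to change.** In SAP 2.5.2:

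- Add by-occasion related-AE tables (SOC/PT, maximum intensity, action taken) limited to onset within 28 days after each injection session. Show the Day 1 session, touch-up and re-treatment in separate columns, each with the number of subjects injected at that session as denominator.
- Keep the full-period related-AE table as a separate table with observation time shown.
- Summarise days to onset by occasion, with a footnote that scheduled observation after re-treatment is about 4 weeks and is uninformative for later onset.
- Treat any contrast restricted to subjects with both occasions as supplementary, and label it as a self-selected subset.

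With this change, each column has a nominal 4-week window and one session, so the window ratio falls from 12–13 to 1. The corrected percentages cannot be predicted from the documents.

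The cost is SAP wording and one extra table set from AE start dates, injection dates and visit dates already collected. Visits and treatment do not change. The downside is that events after day 28 appear only in the full-period table.
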